9.4.2 Secondary endpoints

A sequential (closed) testing procedure will be used to control the overall type I error rate. Formal testing of the first secondary endpoint will be undertaken only if a statistically significant result is achieved on the primary endpoint of OS in the Child Pugh A population and formal testing of the second secondary endpoint will be undertaken only if a statistically significant result is achieved on the first secondary endpoint.

1. Progression Free Survival (PFS):

PFS is defined as the time from the date of randomisation to the date of the first documented progression or death from any cause. The assessment of progression will be done by an independent radiological review according to RECIST 1.1. Patients without progression or death at the end of study treatment period will be censored at the date of their last tumour assessment.

PFS will be analyzed in the ITT Child Pugh A population with an additional analysis in ITT and PP populations.

Definition of date of progression or censoring will refer to FDA guidelines for PFS.

PFS will be estimated using the Kaplan-Meier method and plotted as curves by treatment group. The comparison between groups (pooled DT 20mg/m² and 30mg/m² versus BSC) will be made using LogRank test.

HR, median and mean survival and PFS rates every 2 months will be given with the corresponding 95% confidence intervals.

If the primary endpoint of OS is statistically significant for the pooled DT 20 mg/m² and 30mg/m² groups versus BSC in the Child Pugh A population, PFS will be formally tested at significance level of 5% for the pooled DT 20 mg/m² and 30mg/m² group versus BSC in the Child Pugh A population. The analysis of the other comparison will be considered as exploratory.

In addition to the analysis not adjusted for baseline characteristics considered above, a sensitivity analysis will be conducted using a model adjusting for geographical region and pre-defined selected prognostic factors as recently described in this population such as ECOG score, BCLC stage and macroscopic vascular invasion, extrahepatic spread and hepatic impairment

(Child Pugh score, prothrombine time) (Marrero J.A., 2013^[54], Reig M., 2013^[55], Iavarone M., 2015^[56]).

2. Objective Response Rate (ORR):

ORR is defined as the proportion of patients whose best overall response is complete or partial response during the study treatment period. The assessment of tumour response will be done by an Independent Radiological Review according to RECIST 1.1.

ORR will be analyzed in the ITT Child Pugh A population with an additional analysis in ITT and PP populations.

The comparisons between groups (pooled DT 20mg/m² and 30mg/m² versus BSC) will be made using chi-square test.

If the PFS is statistically significant for the pooled DT 20mg/m² and 30mg/m² group versus BSC in the Child Pugh A population, ORR will be formally tested at significance level of 5% for the pooled DT 20mg/m² and 30mg/m² group in the Child Pugh A population. The analysis of the other comparison will be considered as exploratory.

In addition to the analysis not adjusted for baseline characteristics considered above, a sensitivity analysis will be conducted using a model adjusting for geographical region and pre-defined selected prognostic factors as recently described in this population such as ECOG score, BCLC stage and macroscopic vascular invasion, extrahepatic spread and hepatic impairment (Child Pugh score, prothrombine time) (Marrero J.A., 2013^[54], Reig M., 2013^[55], Iavarone M., 2015^[56]).

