17. Patients who have received an experimental drug in another clinical trial in the last 30 days prior to randomisation in the present clinical trial; 18. Women of child-bearing age who are unwilling or unable to use an effective contraception method (oral contraception or intra-uterine device for woman) during the study treatment period and for 6 months after the last administration of study drug, and their male partner(s) refusing to use a condom (if applicable), Men who are unwilling or unable to use a condom during the study treatment period and for 6 months after the last administration of study drug, and their female partner(s) refusing to use one of the appropriate effective contraception methods (if applicable); 19. Patients unwilling or unable to comply with protocol requirements and scheduled visits.		
Randomisation : Randomisation will be performed using IWRS with stratification per region		
Drug Being Tested, Dose, Method of Administration :		
Product name: Unit dose: Regimen: Mode/route:	Doxorubicin Transdrug™ 10 mg (DT) Two dose levels: 20 mg/m ² and 30 mg/m ² Once every 4 weeks Slow IV Infusion over 6 hours	
Study treatment period: 
 The patients randomised in Doxorubicin Transdrug™ groups will be hospitalized or will have an outpatient visit on D0 to check eligibility criteria for continuing treatment and to ensure that the premedication will be taken. Patient will receive DT infusion on D1 and will be hospitalized until D2. Patient could be discharged on D2 or on D3 in the absence of toxicity. Study treatment will be repeated every 4 weeks until unequivocal progression (assessed by the investigator) or unacceptable toxicity. Study visits will be performed at the beginning of each cycle, at day 14 of each cycle and one month after the last study drug administration (end of study visit). The patients randomised in control group will receive the Best Standard of Care per local practice. Study visits in the control group will be performed at the same schedule than in the DT arms on each cycle initiation, day 14 and one month after the last study drug administration (end of study visit). 		
Duration of Treatment: In all groups, until disease progression or unacceptable toxicity. For patient randomised in Doxorubicin Transdrug™ group, the total dose of Doxorubicin or equivalent will not exceed 550 mg/m ² (this takes into account prior anthracyclins cumulative dose and DT cumulative dose).		

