
– Objective Response Rate (ORR) by the Independent Radiological Review according to RECIST 1.1
 
Exploratory efficacy endpoints*:
 
 – Progression-free survival by the investigator’s evaluation according to RECIST 1.1; – Objective Response Rate by the investigator’s evaluation according to RECIST 1.1; – Time To Progression (TTP), Best Overall Response and Disease Control Rate; – Time to Objective Response and Duration of Response; – Evolution in serum α-fetoprotein levels (AFP). 
*PFS and ORR will be analyzed by the investigator evaluation according to RECIST 1.1 and according to modified RECIST for HCC (if possible), and by the Independent Radiological Review according to the modified RECIST for HCC (if possible). TTP, Best Overall Response, Disease Control Rate, time to objective response and duration of response will be analyzed by the Investigator Evaluation and by the Independent Radiological Review, according to RECIST 1.1 and according to modified RECIST for HCC (if possible).
 
Safety endpoints:
 
Respiratory:
 
 – Incidence and duration of reduction of SaO2 during DT infusion (in DT arms); – Incidence and severity of respiratory events; 
Cardiac
 
 – Incidence and severity of cardiovascular events (including BP and HR); – ECG and LVEF change; 
Overall
 
 – Incidence and severity of all TEAEs and SAEs according to NCI-CTCAE v4.0 scale; – Biological (haematology and biochemistry analyses, and particularly AST/ALT, WBC). 
Pharmacokinetic endpoints (in selected sites for PK):
 
 – Pharmacokinetic profile of Doxorubicin and its metabolites; – Relationship between efficacy and safety (e.g., clinical, biological) parameters, concentrations of total and free doxorubicin and doxorubicinol and blood biomarkers 
Quality of Life:
 
 – EuroQoL EQ-5D questionnaire to be completed by patients during the study treatment period: at baseline, then every 2 cycles and finally, at progression or at the latest, if treatment is stopped for other-than-progression reasons (e.g., end of study visit) 		

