3 TRIAL DESIGN

This is a multicentre, open-label, randomised, comparative, 3 arms (DT 20 mg/m², DT 30 mg/m², Best Standard of Care) study in patients suffering from hepatocellular carcinoma.

The study will be carried out at multiple hepatology or oncology centres that manage patients with HCC with or without cirrhosis. Approximately 100 centres will be involved in the trial.

Based on the survival data obtained in the phase II clinical trial, it has been calculated that 390 patients have to be included to adequately compare the efficacy of DT 20 mg/m² and DT 30 mg/m² to that of BSC.

A safety evaluation will be carried out on a regular basis at least twice a year by the Data Safety Monitoring Board (DSMB) and every 75 patients (around 25 patients/group) whichever comes first.

Patients who meet the inclusion/exclusion criteria will be randomised according to a 1:1:1 ratio to receive either DT 20 mg/m², DT 30 mg/m², or BSC. Only those patients whose survival expectations is longer than 2 months and could receive more than 1 DT infusion will be enrolled.

The study duration for each patient includes a screening period of 28 +/- 2 days maximum before baseline visit (D0 Cycle 1). The patient will then be randomised to receive either DT 20 mg/m² or DT 30 mg/m² as protracted IV infusion over 6 hours once every 4 weeks or BSC.

Patients will receive study therapy until unequivocal tumour progression (assessed by the investigator) or occurrence of unacceptable toxicity.

All patients will be evaluated by CT scan or MRI every 2 months for tumour assessments.

After study therapy discontinuation, an end of study visit will be performed 1 month +/- 7 days after the last DT infusion or last BSC treatment.

Then, a follow up of all patients (including those who withdrew prematurely from the study) will be maintained every 3 months until death. The following information will be recorded:

- Survival (patient alive or deceased)
- Date of progression (in the case of withdrawal for other reason than progression during the study treatment period)
- Administration of any other anti-cancer treatment.

The follow-up period is defined as “until 2 years after Last Patient In”.

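### PFS counts death from any cause but is censored at the end of each patient's treatment period, so later progressions and deaths are dropped, possibly informatively and unequally by arm

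*Combined protocol and SAP*

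**What the plan says.** Section 9.4.2 sets the event: "PFS is defined as the time from the date of randomisation to the date of the first documented progression or death from any cause". The assessor follows: "The assessment of progression will be done by an independent radiological review according to RECIST 1.1". The censoring rule is: "Patients without progression or death at the end of study treatment period will be censored at the date of their last tumour assessment". One further sentence bears on it: "Definition of date of progression or censoring will refer to FDA guidelines for PFS". It names no option within that guidance and does not say which text prevails.

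Other sections matter for reading this rule:

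- **Primary endpoint (9.4.1).** OS is censored at the time of the statistical analysis, not at the end of treatment.
- **Treatment duration (Synopsis).** "In all groups, until disease progression or unacceptable toxicity". Under section 3 it is the investigator who assesses that progression.
- **Dose delay (6.6.2).** A DT patient who still fails a continuation criterion after a four-week delay leaves the study treatment period. The term therefore applies to the individual patient.
- **Follow-up (3).** All patients, including early withdrawals, are followed every 3 months until death. Survival, other anticancer treatment and, for withdrawals not due to progression, the progression date are recorded.
- **Imaging (3).** "All patients will be evaluated by CT scan or MRI every 2 months for tumour assessments".
- **Role in testing (9.4.2).** PFS in Child-Pugh A patients is formally tested at 5% after OS succeeds in the ITT and Child-Pugh A populations. It gates ORR.

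The same censoring wording appears in section 9.4.3 for exploratory PFS, TTP, time to objective response and duration of response.

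**The concern.** The event definition and the censoring rule describe different quantities. The first is time to progression or death. The second observes that time only while the patient is in the treatment period. Events after a stop for any other reason are discarded, although most of the data needed to count them are collected.

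Log-rank and Kaplan-Meier analyses assume that censored patients have the same later risk as those who remain. A patient taken off treatment because liver, respiratory or blood criteria are not met may well be deteriorating. If such stops are more frequent in one arm, the comparison is distorted. If they are equally frequent, events and power are still lost. As written, the PFS result depends partly on when treatment was stopped in an open-label trial.

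**Working it through.** **1. Is the period patient-level?** Yes. Section 6.6.2 withdraws individuals from it, and the Synopsis ends treatment at the patient's own progression or toxicity. Its exact end is unclear. The Synopsis visit schedule and quality-of-life text suggest the visit one month after the last administration, while section 6.6.2 suggests the decision to withdraw. For BSC, which may be supportive care only (6.4), the end is less clear still.

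**2. Can stopping differ by arm?** Setting the sections side by side:

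- DT has dose-level floors, a four-week delay limit and a cumulative cap (6.6.1–6.6.3). BSC follows local practice (6.4, 6.6.4).
- Of the 8 prohibited treatment categories in section 6.9, 2 apply to all patients and 6 to DT only. Needing a prohibited medication is a possible reason for removal (4.4).
- The cap of 550 mg/m² includes prior anthracycline, and up to 300 mg/m² prior is admissible. Full-dose infusions available: 550/20 gives 27 and 550/30 gives 18 with no prior dose; 250/20 gives 12 and 250/30 gives 8 with 300 mg/m² prior. Stops at the cap occur only in patients who have been event-free for a long time.
- Treatment ends on the investigator's call, but the event needs independent review. A call that central review does not confirm also ends in censoring.

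Some DT stops may therefore mark worsening, while others mark long benefit. They pull in opposite directions.

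**3. The plan's own figures.** There is no PFS event count, power or stopping rate to reproduce. For OS, the Schoenfeld formula with 285 events, HR 0.69 and 2:1 allocation gives √(285 × 2/9) × |ln 0.69| − 1.96 = 7.958 × 0.3711 − 1.96 = 0.993, a power of 84.0% against the stated 85%.

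**4. Events and power with equal stopping.** From the documents: 85% of 390 = 331 Child-Pugh A patients (110 BSC, 221 DT), 2-monthly scans and control median OS of 9 months. Assumed: median PFS 3 months, 20% of PFS events being deaths, 10–30% stopping before an event, and PFS HR 0.68 borrowed from OS. By simulation, counting every event gives about 316 events and about 89% power. The written rule loses about 20–95 of them (20/316 = 6%; 95/316 = 30%), and power falls to roughly 70–86%. The lower event loss applies if counting runs to the one-month visit, the higher if it ends at the stop.

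The same formula gives a rough check:

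- 316 events: 8.380 × 0.3857 − 1.96 = 1.272, power 90%
- 296 events: 8.110 × 0.3857 − 1.96 = 1.168, power 88%
- 221 events: 7.008 × 0.3857 − 1.96 = 0.743, power 77%

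The formula makes no allowance for 2-monthly detection or for dating censoring back to the last scan.

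**5. Direction with unequal stopping and no true effect.** If BSC stops half as often as DT, counting all events gives HR 1.00. Under the written rule the HR falls below 1 if the hazard is 2–3 times higher after the stop, and stays at about 1.00–1.04 if it is unchanged. In a second model, stopping hazards were 0.10 (DT) and 0.03 (BSC) per month with unchanged risk. The HR moved from 1.00 to 1.07 and events fell from about 330 to 252.

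**6. The replacement rules.** In the first model, using section 3 follow-up dates for every stopped patient gives HR 0.99–1.00. Central reads plus deaths, with no scans after the stop, gives 0.87–0.97, worse than the present rule: stopped patients stay at risk with death as their only possible event.

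**The case against.** The strongest reply is that the visible text is not the whole plan. Section 9.4.2 refers to FDA guidelines, section 9.1.1 defers details and missing data to a separate SAP, and sections 5.2 and 7.2.1–7.2.5 cannot be read. The matter may be settled there. This limits confidence. It does not remove the point, because the explicit censoring sentence stands beside a general reference that does not override it. The PFS sensitivity analysis in section 9.4.2 changes covariates, not censoring.

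Second, the consequence is bounded. PFS is third in the sequence, so if DT has no OS effect the OS tests already cap the error. Inflation of the PFS test matters only if DT prolongs OS without affecting PFS. This stands. The loss of power, however, falls exactly where OS has succeeded.

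Third, counting later events mixes centrally reviewed progression with follow-up dates that need not be radiological. This also stands, and is the real price of the change.

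A reader might infer that the rule favours DT or inflates the error by a known amount. The documents do not support that: they give no stopping rates or risk after stopping, and stops go both ways. With 30% stopping and a threefold later hazard, repeat simulations gave one-sided errors from 4.9% to about 8% with the one-month reading and from 6.8% to about 13% with counting to the stop. No single value should be quoted as firm. A reader might also infer that 2-monthly scans continue after treatment. The section 3 follow-up list contains no imaging, so this is not established.

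**Conclusion.** The inconsistency is in the text and needs no simulation: the PFS definition includes events that the censoring rule discards. That the censoring may be informative and may differ by arm follows from the arm-specific stopping rules. Its size and direction cannot be determined from the documents.

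The most stable quantitative result is the loss of about 6–30% of PFS events, with the accompanying loss of power, under the assumed stopping rates. The HR shifts illustrate what could happen and are not predictions. OS and the sample size are untouched. This should be corrected before database lock because PFS is formally tested and gates ORR. Confidence is medium, since the separate SAP and several sections cannot be read.

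**What to change.** - **Censoring rule.** In section 9.4.2, and in 9.4.3 for exploratory PFS and TTP, remove the reference to the end of the study treatment period. For PFS, count the first progression or death from any cause up to the data cut-off regardless of treatment stop. Censor event-free patients at the last evaluable assessment before the cut-off. State that this rule governs alongside the FDA reference.
- **Source of progression.** Use independently reviewed progression where scans exist. Where a patient stopped for another reason and has no later central scan, use the section 3 follow-up date.
- **Unconfirmed investigator progression.** Section 3 collects no follow-up progression date for these patients. Count their deaths, as the definition requires. Show censoring at the last scan and use of the investigator's date as sensitivity analyses. If such calls are twice as frequent in one arm (5% against 10% per scan, assumed), the HR under no effect is 0.96–1.04 with deaths only, 0.98–1.01 with censoring and 0.91–1.09 with the investigator's date.
- **Other sensitivity analyses.** Keep the present rule, central reads plus deaths only, and censoring at new anticancer therapy.
- **Related endpoints.** Apply the same cut-off logic to time to objective response and duration of response, or say why not. Define the end of the study treatment period for each arm, since ORR still uses it.

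The cost is wording in section 9.4 and the SAP, plus central reading of any later scans that sites do not already send. The downside is that some progressions after the stop will be investigator-dated at 3-monthly contacts in an open-label trial.

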9.4.3 Exploratory endpoints

No adjustment for multiple testing will be performed in the analysis of exploratory endpoints and p-values will be interpreted as exploratory.

All exploratory analyses will be conducted in ITT and ITT Child Pugh A population.

1. PFS by the Independent Radiological Review according to mRECIST is defined as the time from the date of randomisation to the date of the first documented progression or death from any cause. Patients without documented progression or death at the end of study treatment period will be censored at the date of their last tumour assessment.

PFS will be estimated by the Kaplan-Meier method and plotted as curves by treatment group. The comparison between groups (pooled DT 20mg/m² and 30mg/m² versus BSC) will be made using LogRank test.

2. PFS by the investigator according to RECIST 1.1 (and mRECIST if possible) is defined as the time from the date of randomisation to the date of the first progression (documented or clinical) or death from any cause. Patients without progression or death at the end of study treatment period will be censored at the date of their last tumour assessment.

PFS will be estimated by the Kaplan-Meier method and plotted as curves by treatment group. The comparison between groups (pooled DT 20mg/m² and 30mg/m² versus BSC) will be made using LogRank test.

3. ORR by the independent radiological review according to mRECIST is defined as the proportion of patients whose best overall response is complete or partial response during the study treatment period.

The comparison between groups (pooled DT 20mg/m² and 30mg/m² versus BSC) will be made using chi-square test .

4. ORR by the investigator according to RECIST 1.1 (and mRECIST if possible) is defined as the proportion of patients whose best overall response is complete or partial response during the study treatment period.

The comparison between groups (pooled DT 20mg/m² and 30mg/m² versus BSC) will be made using chi-square test.

5. Time To Progression (TTP):

TTP is defined as the time from the date of randomisation to the date of the 1st documented progression or death related to tumour progression. The assessment of progression will be done by the independent radiological review according to RECIST 1.1 and mRECIST (if possible) and by the investigator according to RECIST 1.1 and mRECIST (if possible). Patients without progression at the end of study treatment period will be censored at the date of their last tumour assessment.

Definition of date of progression or censoring will refer to FDA guidelines for TTP.

TTP will be estimated by the Kaplan-Meier method and plotted as curves by treatment group. The comparison between groups (pooled DT 20mg/m² and 30mg/m² versus BSC) will be made using LogRank test.

6. Best Overall Response and Disease Control Rate:

The assessment of tumour response will be done by the Independent Radiological Review according to RECIST 1.1 and mRECIST (if possible) and by the investigator according to RECIST 1.1 and mRECIST (if possible).

Best Overall Response is defined as the best response observed during the study treatment period (no requirement for confirmation).

Disease Control Rate is defined as the proportion of patients whose Best Overall Response is complete response, partial response or stable disease during the study treatment period.

The comparison between groups (pooled DT 20mg/m² and 30mg/m² versus BSC) will be made using chi-square test.

7. Time to Objective Response:

Time to Objective Response will be calculated from randomisation to the date to first documented objective response (CR or PR). Patients without documented response (CR or PR) at the end of study treatment period will be censored at the date of their last tumour assessment. The assessment of tumour response will be done by the Independent Radiological Review according to RECIST 1.1 and mRECIST (if possible) and by the investigator according to RECIST 1.1 and mRECIST (if possible).

8. Duration of Response:

Duration of response will be calculated in the subpopulation of patients experiencing a response (CR or PR) from the time when objective response (CR or PR) is first met to the date of first documented progression. The assessment of tumour response and progression will be done by the Independent Radiological Review according to RECIST 1.1 and mRECIST (if possible) and by the investigator according to RECIST 1.1 and mRECIST (if possible). Patients without documented progression at the end of study treatment period will be censored at the date of their last tumour assessment.

Duration of Response will be estimated only for patients achieving an objective response using the Kaplan-Meier method and plotted as curves by treatment group.

9. Evolution in serum α -foetoprotein levels (AFP):

Serum AFP levels will be summarized by visit and by dose. Differences between AFP levels every other month and at baseline will be summarized as well. Comparisons between groups will also be made using non parametric tests. The number of patients with a decrease in AFP from baseline will be shown overall and by dose of DT.

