8.7.3 Progression of underlying malignancy

Progression of underlying malignancy is not reported as an AE if it is clearly consistent with the suspected progression of the underlying cancer as defined by RECIST or mRECIST criteria or based on clinical progression assessed by the investigator.

Death or hospitalization due solely to the progression of underlying malignancy should NOT be reported as a SAE.

Clinical symptoms of progression may be reported as AEs if the symptom cannot be determined as being exclusively due to progression of the underlying malignancy, or does not fit the expected pattern of progression for the disease under study.

Progression could be evident in the patient's clinical symptoms, and the investigator may elect not to perform further disease assessments. In such cases, the progression is based on symptomatic deterioration and considered as a clinical progression. As far as possible, these evaluations should be a rare exception and every effort should be made to document the progression.

If there is any uncertainty about an AE or SAE being due ONLY to the progression of the underlying malignancy, it should be reported as an AE or SAE.

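### Investigator PFS counts clinical progression under a RECIST 1.1 label, but investigator duration of response, and TTP on its natural reading, do not (exploratory endpoints; minor)

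*Combined protocol and SAP*

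**What the plan says.** Three investigator-assessed endpoints in section 9.4.3 depend on a progression date.

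- **PFS (item 2).** The label and start point are "PFS by the investigator according to RECIST 1.1 (and mRECIST if possible) is defined as the time from the date of randomisation". The endpoint runs to "the date of the first progression (documented or clinical) or death from any cause". The censoring rule is "Patients without progression or death at the end of study treatment period will be censored at the date of their last tumour assessment".
- **TTP (item 5).** One definition serves both the independent review and the investigator. The event is "the date of the 1st documented progression or death related to tumour progression". The censoring rule is "Patients without progression at the end of study treatment period will be censored at the date of their last tumour assessment".
- **Duration of response (item 8).** Again one definition serves both assessors. It runs from first response "to the date of first documented progression". Responders with no documented progression by the end of the treatment period are censored at their last tumour assessment.

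Section 8.7.3 explains the clinical category. The investigator may choose to do no further disease assessment, and then "the progression is based on symptomatic deterioration and considered as a clinical progression". The same section asks that this be a rare exception and that progression be documented wherever possible. Appendix IX makes RECIST 1.1 and mRECIST progression a CT or MRI finding.

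**The concern.** For one assessor and one named criterion, the plan uses two meanings of progression. A clinical progression as described in section 8.7.3 is not an imaging event, so a PFS that counts it is not strictly a RECIST 1.1 PFS. The endpoints beside it, under the same label, leave it out.

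The censoring this produces is not neutral. A responder censored for duration of response because progression was clinical only has just been judged to be progressing. Kaplan-Meier estimates treat that patient as having the same outlook as responders still under observation, so the estimated duration is too long. TTP is exposed to the same problem if its ambiguous censoring sentence is read in the natural way. A reader who sets the investigator PFS and TTP tables side by side would also find that they differ by more than non-tumour deaths, with nothing in the plan to explain it.

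**Working it through.** The plan gives no figure to reproduce. The check compares the rules, applies them to a constructed patient, and then bounds the size.

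**1. Rules side by side (investigator, RECIST 1.1)**

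| Endpoint | Clinical progression a listed event? | Patient with clinical progression only |
|---|---|---|
| PFS, item 2 | Yes | Event at the clinical date |
| TTP, item 5 | No; tumour-related death is listed | Not a listed event; censoring sentence says only without progression, so unclear |
| Duration of response, item 8 | No | Censored at last tumour assessment (responders only) |

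Item 1 (independent-review PFS by mRECIST) uses the word documented in both its event and its censoring sentence. Item 2 adds the clinical category and drops that word from its censoring sentence. Nothing in the visible text carries the investigator-specific rule over to items 5 and 8, or says that the difference is intended.

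**2. Constructed patient.** Section 3 schedules imaging every 2 months. Suppose partial response at month 2, maintained at month 4, clinical progression at month 5, and no further scan.

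- PFS: event at month 5.
- Duration of response: censored at month 4, that is 4 − 2 = 2 months after response onset.
- TTP: no listed event at month 5. The natural reading is censoring at month 4, unless a later tumour-related death is counted. Because censoring is tied to the end of the study treatment period, it is unclear whether a death after that period counts.

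A non-responder shows the same split between PFS and TTP and does not enter duration of response.

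**3. Would a later scan close the gap?** Not by plan. Section 3 ends study therapy at investigator-assessed progression. In follow-up it records a progression date only for patients withdrawn for some other reason. No later radiological date is planned for a patient stopped for clinical progression.

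**4. Size.** Let c be the share of progressions that are clinical only and are censored. The plan gives no value, so c is an assumption. With constant hazard λ:

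- hazard seen after censoring = (1 − c)λ
- median = ln 2 / hazard, so the median is multiplied by 1/(1 − c)
- c = 5%: 1/0.95 = 1.053, about 5% longer
- c = 10%: 1/0.90 = 1.111, about 11% longer

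This is a ceiling for single-arm TTP, because counted tumour-related deaths restore some of the lost events. For the comparison of pooled DT with BSC, the observed hazard ratio is the true ratio × (1 − c in DT)/(1 − c in BSC). Equal shares cancel.

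**The case against.** The strongest reply is that little depends on this. Section 9.4.3 declares these endpoints exploratory, with p-values read as such. The formally tested PFS in section 9.4.2 uses independent review and documented progression. Dose selection in section 9.6 rests on OS and on discontinuations and deaths from adverse reactions. Section 8.7.3 expects clinical progression to be rare. All of this stands and sets the severity.

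It can also be said that the wording in item 2 is explicit and may be deliberate, that item 5 refers dates to FDA guidance, and that section 9.1.1 leaves detail to a separate SAP. Sections 5.3 and 7.2.3 are redacted or not shown and could hold reconciling text. That is fair, but the visible definitions still differ, and a deliberate difference should be stated.

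Three stronger readings are tempting and are not supported:

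- **A planned investigator-versus-independent PFS comparison is spoiled.** No such comparison is planned. Each version is analysed as pooled DT against BSC.
- **Clinical progressors are certainly censored for TTP.** The TTP text lists tumour-related death as an event, and its censoring sentence is ambiguous. Clear censoring is shown only for duration of response.
- **The treatment effect is biased.** The open-label design makes unequal shares conceivable, but the documents give no shares by arm. Equal shares leave the hazard ratio unchanged under the constant-hazard model.

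A last objection concerns the remedy: a documented-only main definition keeps the informative censoring and brings it into investigator PFS. That is correct. The paired sensitivity analysis is what reveals the effect; the aligned main definition only makes the labels and tables consistent.

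**Conclusion.** The point holds as a minor inconsistency of definition. Under one RECIST 1.1 label, the same investigator judgement is an event for PFS, informative censoring for duration of response (responders only) and, on the natural reading, censoring for TTP unless a tumour-related death is counted. The affected single-arm estimates would tend to be too long.

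The number of patients cannot be derived from the documents. The illustrative TTP inflation of at most about 5% to 11% rests on an assumed share of 5% to 10% and a constant hazard. No size was worked out for duration of response. OS, the formally tested independent-review PFS, alpha, sample size and dose selection are not touched.

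**What to change.** Make these changes in section 9.4.3 and in the SAP, which section 9.1.1 says is finalised before database lock:

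1. Use one progression definition for investigator PFS, TTP and duration of response. Any version labelled RECIST 1.1 or mRECIST should count documented radiological progression, together with the deaths that each endpoint already lists.
2. For all three, report a sensitivity analysis that counts clinical progression as an event at its date. Relabel the current item 2 PFS as the PFS member of that set.
3. Align the TTP censoring sentence with its event definition by referring to documented progression, and state whether a tumour-related death after the study treatment period counts.
4. If the difference is intended, say so and qualify the RECIST 1.1 label in item 2.

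The cost is wording and a few extra exploratory tables. Item 2 already needs the clinical progression date, so no new data are required. The downside is that documented-only investigator PFS will also censor clinical progressors, so the sensitivity analysis should be shown beside it.
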